APPENDIX 9: Randomisation, concealment and code-break

APPENDIX 10: Participant withdrawal

APPENDIX 11: References

1. TRIAL SYNOPSIS

Short trial title	Children's ear drops for ear pain in acute otitis media: the CEDAR Randomised
	Controlled Trial and Observational Cohort Study.
Scientific trial title	What is the clinical and cost effectiveness of benzocaine/phenazone ear drops for
Scientine that the	reducing antibiotic consumption in children aged between 12 months and 10 years
	presenting to primary care with acute otitis media (AOM)?
Phase	IV
Sponsor Chief Investigator	University of Bristol
Chief Investigator	[name]
ISRCTN	ISRCTN09599764
EudraCT No.	2014-004016-11
REC Reference	To be provided
Medical condition	Acute otitis media (AOM)
under	
investigation	
Purpose of trial	The main aim of the CEDAR trial is to investigate the clinical and cost effectiveness of
	benzocaine/ phenazone (hereon 'active') ear drops compared to 'no drops' (usual care)
	for reducing antibiotic consumption in children aged between 12 months and 10 years
	presenting to primary care with AOM.
	The trial will also investigate the clinical and cost effectiveness of active ear drops
	compared to placebo drops for ear pain.
Main research	Primary research question:
question (primary	1.1 Do active drops lead to a lower proportion of children consuming antibiotics by Day
objective)	8 (where Day 1 is the day of randomisation) compared with no drops (usual care)?
Other research Key secondary research question:	
questions2.1. Do active drops provide superior pain relief in the first 24-36 hours comp	
(secondary	placebo drops?
objectives)	
	Other secondary research questions:
	2.2. Do active drops lead to reduced oral analgesic consumption in the first 7 days after
	randomisation (where Day 1 is the day of randomisation) compared with placebo
	drops?
	2.3. Do placebo drops provide superior pain relief in the first 24-36 hours after
	randomisation compared to 'no drops' (usual care)?
	2.4. Do active drops provide superior pain relief during Day 1 (day of consultation)
	compared to placebo drops? (Measured at approximately 1 hour after
	administration of the drops and on the evening of Day 1)
	2.5. Do active drops lead to a lower proportion of children consuming antibiotics by Day
	8 post randomisation compared with placebo drops?
	2.6. Do active drops alter the number of days before starting antibiotics in the first
	seven days after randomisation, compared with placebo drops and no drops (usual
	care)?

	2.7. Do active drops reduce overall symptom burden (including episodes of crying/ distress, disturbed sleep, interference with normal activity, appetite and fever) in the first 7 days after randomisation compared to placebo drops and no drops (usual care)?	
	2.8. Do active drops alter overall illness duration (defined as the last day post randomisation on which parent-reported child ear pain scores zero for two consecutive days without other analgesic medication) compared to placebo drops and no drops (usual care)?	
	2.9. What are the net incremental costs to the NHS (e.g. fewer antibiotic prescriptions) and society (e.g. parental productivity) of using active ear drops compared to no drops (usual care) in the short (7 days) and medium term (3 months) post randomisation?	
	2.10. To conduct an economic analysis to explore whether the net incremental costs of active ear drops are justified by improved pain relief, symptom burden, antibiotic use or quality of life.	
	2.11. To use qualitative methods to investigate parent and clinicians' views, experiences and acceptability of the diagnosis and treatment of AOM in the CEDA trial.	
	2.12. To investigate the representativeness of the CEDAR trial sample by describing the presentation, management and outcome of children with AOM in primary care.	
Trial design	Individually randomised, three arm (active, placebo and no drop) superiority trial with cost effectiveness analysis and cost consequence study, and nested qualitative evaluation. Two control groups: (i) no drop (usual care, open design), because parental administration of antibiotics may be influenced by the parent's knowledge of the intervention as well as its effectiveness; and (ii) placebo, as recommended by the 2011 Cochrane Review ¹ because placebo drops may have a soothing effect, and because the pain outcome is reported by parents (subjective). In addition, an observational prospective cohort study of children not included in the trial in order to assess external validity.	
Trial participants	Children aged between ≥ 12 months and <10 years with ear pain due to acute (including recurrent) otitis media.	
Inclusion criteria	 Trial inclusion criteria (all criteria must be met): Aged ≥ 12 months and <10 years Presenting within 1 week of suspected AOM onset (other preceding respiratory tract infection symptoms may be longer) Parent/legal guardian available to give consent Parent-reported ear pain in 24 hours pre-enrolment (or parent-suspected ear pain if child is too young to report pain) Clinician diagnosis of acute otitis media (although not an entry criterion, clinicians will be asked to report the presence of otoscopic evidence of acute tympanic membrane inflammation, operationalised as per our previous trial⁶ as: erythema with dullness or cloudiness; or bulging) Child is immunocompetent 	

	 Clinician willing to use a NICE-recommended 'no' oral antibiotic prescribing strategy or a 'delayed' oral antibiotic prescribing strategy (as per NICE guidelines) for the AOM and other elements of the underlying acute respiratory tract infection. NICE recommends a 'no' or 'delayed' antibiotic prescribing strategy for most immune-competent children with acute otitis media. Parent able to give ear drops. Parent willing in principle to use ear drops before oral antibiotics and to wait before giving delayed antibiotics as per NICE guidelines. Parent able to report the child's ear pain. Parent able and willing to complete daily Symptom and Recovery Questionnaire in the English language, and receive regular follow-up telephone calls, in the English language, today and every 2-3 days for up to 7 more days (or until child has been free of ear pain without medicines for two days running).
	Observational study inclusion criteria (all criteria must be met):
	12) Aged \geq 12 months and <10 years
	 13) Presenting within 1 week of suspected AOM onset (other preceding respiratory tract infection symptoms may be longer)
	14) Parent/legal guardian available to give immediate written or (if not present) telephone consent, and to provide written consent within 24 hours
	15) Parent-reported ear pain in 24 hours pre-enrolment (or parent-suspected ear pain if child is too young to report pain)
	 16) Clinician diagnosis of acute otitis media (although not an entry criterion, clinicians will be asked to report the presence of otoscopic evidence of acute tympanic membrane inflammation, operationalised as per our previous trial⁶ as: erythema with dullness or cloudiness; or bulging) 17) Child is immunocompatient.
	 17) Child is immunocompetent. 18) Parent does not want to use trial ear drops (reason to be recorded). 19) Parent does not want to take part in the RCT (reason to be recorded).
	 20) Parent able to report the child's ear pain. 21) Parent able and willing to complete daily Symptom and Recovery Questionnaire in the English language, and receive regular follow-up telephone calls, in the English language, today and every 2-3 days for up to 7 more days (or until child has been free of ear pain without medicines for two days running)
Exclusion criteria	Trial exclusion criteria (presence of any warrants exclusion):
	 Child requires immediate hospitalisation Child requires same day oral antibiotic treatment for AOM or other elements of the underlying acute respiratory tract infection (assess these children for observational study eligibility). NICE recommends same day antibiotic treatment for:
	2.1) Child younger than 2 years with bilateral acute otitis media2.2) Otorrhoea (discharge from the ear)
	2.3) Child systemically very unwell or showing signs of respiratory distress (e.g. tachypnoea, hypoxia or recession)2.4) Child has symptoms and signs suggestive of serious illness and/or
	 complications (particularly mastoiditis) 2.5) Child is at high risk of serious complications because of pre-existing comorbidity. NICE guidelines recommend the following children are excluded: 2.5.1) Child has significant heart, lung, renal, liver or neuromuscular disease (defined for the purposes of this study as requiring ongoing inpatient or outpatient care from specialist teams)

	2.5.2) Child has immunosuppression (defined for the purposes of this study
	as a formal diagnosis of immunosuppression)
	2.5.3) Child has cystic fibrosis
	2.5.4) Child born prematurely (defined for the purposes of this study as born
	before 34 weeks and presenting within the first year of life)
	NB: Children with other conditions who are at higher risk of AOM (e.g.
	Down's Syndrome, cleft palate) may take part if the Responsible Clinician
	feels that they meet the inclusion criteria above)
3)	Child requires same day oral antibiotics for another (non AOM) infection or
	topical antibiotic ear drops
4)	Child is currently receiving (or has received in the past 7 days) oral or ear drop
	(to the AOM ear) antibiotic treatment
5)	Suspected or confirmed tympanic membrane perforation (due to theoretical and
	unconfirmed risk of ototoxicity from active drops) or grommets still in situ
6)	Known sensitivity to trial medicine (Auralgan) or to its ingredients (benzocaine,
	phenazone, glycerine, hydroxyquinoline sulphate) or similar substances (e.g.
	other ester-type anaesthetics such as procaine, tetracaine)
7)	Known porphyria or haemoglobinopathy or glucose-6-phosphate dehydrogenase (G6PD) deficiency or methaemoglobinaemia
2)	
8)	Known family history of G6PD deficiency (noting that G6DP deficiency is more
	common in African, Asian and Mediterranean populations)
	Current use of sulphonamides or antimalarials or hyaluronidase or St John's Wort
	Child needs to continue taking other medicinal products containing benzocaine
11	Child has proven alternative source(s) of pain other than and more severe than
	the ear symptoms with which they are presenting
12)	Otoscopic appearances (as ascertained by clinician, where possible) consistent
	with observed fever, i.e. likely non-specific viral illness only (e.g. with just a
	slightly perfused or pink drum only)
13)	Child has normal ear drum on examination
14)	Child has otitis externa, or other disorder of the outer ear or tympanic membrane
	for which CEDAR ear drops should not be prescribed, in the AOM ear
15)	Child has a hearing aid and parent feels hearing aid should remain in place in the
	AOM ear
16	Symptoms (i.e. hearing loss and longer duration of illness) more suggestive of a
	diagnosis of otitis media with effusion (glue ear)
17	Child has previously taken part in the CEDAR RCT
18	Child has taken part in any research involving medicines within the last 90 days,
	or any other AOM-related research within the last 30 days
Observ	ational study exclusion criteria (presence of any warrants exclusion):
	Child requires immediate hospitalisation
	Child has proven alternative source(s) of pain, other than and more severe than
_,	the ear symptoms with which they are presenting
3)	Otoscopic appearances (as ascertained by clinician, where possible) consistent
3,	with observed fever, i.e. likely non-specific viral illness only (e.g. with just a
	slightly perfused or pink drum only)
A)	Child has normal ear drum on examination
-	Child has otitis externa or other disorder of the outer ear or tympanic membrane
5)	in the AOM ear
6)	Child has a hearing aid and parent feels hearing aid should remain in place in the
	AOM ear
7)	
	diagnosis of otitis media with effusion (glue ear)

	8) Child currently taking or has previously taken part in the CEDAR RCT9) Child has taken part in any AOM-related research within the last 30 days
Setting:	GP practices; Walk-in and Out of Hours Centres; and Children's Emergency Departments (which are frequently used as first point of contact for healthcare services), from hereon 'primary care'.
Outcome: primary	 1.1 Any antibiotic consumed by Day 8 (measured using daily Symptom and Recovery Questionnaire with telephone support calls during week 1), where Day 1 is the day of randomisation.
• •	
Outcomes: secondary	 Key secondary outcome: 2.1. Ear pain over first 24-36 hours post randomisation using the parent completed, validated numerical rating scale successfully used in our previous trial⁶ (Symptom and Recovery Questionnaire with telephone support call in first three days).
	Other secondary outcomes:
	 2.2. Daily symptom severity (until illness resolution i.e. child free of ear pain without need for rescue analgesia for two consecutive days, expected by 8 days for most children¹⁷) including episodes of distress/crying, disturbed sleep, interference with normal activity, appetite, fever and hearing problems
	2.3. Child completed Faces Pain Scale-Revised (FPS-R [Hicks et al 2001], for children aged ≥5 years)
	2.4. Adverse events (Symptom and Recovery Questionnaire)
	2.5. Time taken before oral antibiotics started
	2.6. Ear drop and rescue analgesia consumption (Symptom and Recovery Questionnaire)
	2.7. Parent satisfaction with, and opinion of, treatment allocation and future intention to use drops (with/without prior GP consultation if drops were to become available over-the-counter) after 7 days post randomisation
	2.8. Preference based quality of child life measured (baseline, 24-36 hours, 7 days and 3 months post randomisation) using CHU-9D ¹⁸ (for children age ≥5 years)
	2.9. NHS costs up to 7 days after randomisation (Symptom and Recovery Questionnaire) and contacts to 3 months (primary care medical notes review)
	2.10. Child's school/nursery absences, parent lost productivity and other expenses up to 7 days after randomisation (Symptom and Recovery Questionnaire)
	2.11. Child's quality of life (OMQ-14, ¹⁹ for all children aged 2 years and older) at baseline and 3 months after randomisation (postal questionnaire).
	2.12. Qualitative outcomes to assess acceptability, barriers and adherence, a purposeful sample of parents and clinicians will be asked to participate in qualitative interviews to explore experiences of, and attitudes to AOM and its treatment.

Sample size	Assuming a Type II error rate of 0.1 (90% power) and Type I error rate of 0.05 (alpha) the number of children needed in each group (active ear-drops and no- drops) ranges from 92 to 119 to demonstrate a 20% reduction in antibiotic consumption from 80-90% in the control group ^{8 9} to 60-70%. Using the more conservative estimate of 119, and taking into account 20% attrition, this would give a final sample size of 149 per arm. We are also interested in measuring whether the active eardrops reduce pain compared to the non-active ear-drops. Again using 90% power and alpha set at 0.05 a difference of 1.0 on the pain numerical rating scale, using an SD of 2.5 from our previous RCT ⁶ suggests we need 133 children in each of the active and placebo ear drop groups. Due to a delay in the manufacture of the placebo, we will start the trial as a 2 arm pilot (active drops and usual care, vs usual care/no drops), for the first 3 months of the internal pilot period, and introduce the third arm when the placebo is ready. After assuming 20% attrition and equal numbers in the three groups we will need to recruit 167 children per arm (more than for the primary outcome) and therefore 501 children in total to the RCT. We will recruit up to an equal number of children to the Observational Cohort Study (OCS).
IMP, dosage and	Oil based benzocaine (local anaesthetic) with phenazone (analgesic) ear drops given to
route of administration	affected ear(s) every 1 to 2 hours until pain relieved. Both ears will be treated if AOM bilateral and rescue analgesia (oral paracetamol/ibuprofen) permitted and measured.
administration	
Duration of	Treatment with trial IMP (for the two 'ear drops plus usual care' groups) until pain is
treatment of a	relieved (NB: clinicians and parents will receive training to ensure that, should the child
subject Project timetable	experience a tympanic membrane perforation after trial entry, the use of ear drops will be stopped). Based on our previous systematic review ¹⁷ , we anticipate that for 50% of children the duration of treatment until pain relieved will be 3 days, and that 90% of children's symptoms will have resolved by 8 days ¹⁷ . We will ask parents to complete a daily Symptom and Recovery Questionnaire for their child's symptoms for 7 days following the day of randomisation. Parents will also receive telephone calls at four key points within the first 7 days post randomisation to support completion of the Symptom and Recovery Questionnaire: Day 1, Day 2 (24-36 hours, time point for key secondary outcome data collection), Day 6 and Day 8 (time point for primary outcome data collection). If the child's ear pain persists beyond 7 days post randomisation the parent will, if they permit, continue to be contacted by telephone twice weekly, until the child is better, in order to establish the date on which the child's ear pain had resolved for two consecutive days without medication. A review of the child's primary care medical notes will be conducted by primary care site staff at three months post randomisation. Three months post randomisation, parents will be asked to complete a postal questionnaire about the child's quality of life in the previous three months.
Project timetable	Using recent (post pneumococcal vaccine) RCGP seasonally adjusted AOM incidence data, ² each active GP site (based on average list 6500) ³ will recruit between 0.5 and 1.3 children/month (assumes: 20% of presenting children are eligibility checked; 66% eligible; and 25% agree to be randomised). Based on experience of opportunistic recruitment in previous trials, the number of active primary care sites required to recruit 501 children is estimated to be in the range 80 -120. Due to delays in IMP procurement, recruitment will open by September 2016 and continue until the sample size has been achieved, with the first 8 trial months as an internal pilot phase, beginning with a 2 arm pilot (active drops and usual care, vs usual care/no drops) for the first 3 months, to address a delay in the manufacture of the placebo and to ensure that the trial starts by the time required by the funder.

Team expertise	We are four Senior Academic GPs; an Associate ENT Professor; a Reader in Statistics; a Professor of Health Economics; a Consultant in Paediatric Anaesthesia; a Consultant in Paediatric Emergency Medicine; a Qualitative Researcher and a PPI specialist, who together have considerable experience of successfully completing 'difficult-to-do' randomised trials of interventions for acute infections in children in primary care, including ENT trials
	including ENT trials.

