We want to find out whether pain-killing ear drops can, by treating children's ear pain, reduce the inappropriate prescribing of antibiotics for acute otitis media. The drops we wish to test contain benzocaine (numbing nerve blocker) and phenazone (pain killer). They are believed to work by directly numbing the ear drum. They can be dropped into the ear every 1 to 2 hours and are available over the counter as a pharmacy medicine in Australia, New Zealand and other parts of the world, but not in the UK.

Four previous studies have assessed the effects of single drops, but have proven inconclusive, with experts concluding that a further study is necessary. And no previous study has investigated if repeated doses (the way they are usually used in the home) reduces pain over a longer period (e.g. 24-36 hours), improves quality of life for children, reduces costs or reduces the use of antibiotics. The CEDAR trial (Children's Ear Pain Study) will address all of these issues in children attending primary care with acute middle ear infections.

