5.6. Intervention and placebo

The intervention is an oil based, combined local anaesthetic (benzocaine) and analgesic (phenazone, International Nonproprietary Name, also known in the US as antipyrine) ear drop. One mL contains 14 mg (1.4%) of benzocaine and 54mg (5.4%) phenazone suspended in a glycerine-based liquid along with a preservative (hydroxyquinolone sulphate). Despite an absence of published evidence of effectiveness, it is available as a pharmacy medicine in Australia and New Zealand, and has been marketed since 1947 under Auralgan© (currently manufactured by Pfizer) and other brand names. For this trial we intend to test Auralgan©, manufactured by Pfizer Consumer Healthcare (Australia) and sold in 15mL bottles, or equivalent branded or bespoke manufactured product with the same constituents, against a matched placebo.

The drops are given to the affected ear or ears, according to the instructions provided with the medicine bottle, until pain is relieved - recent published evidence from our group suggests ear pain takes 3 days for 50% of children to resolve and 8 days for 90%.¹⁷ For children with bilateral AOM, parents will be advised to treat both ears simultaneously. Parents will be given detailed instructions on how to give the ear drops, how much to administer and how often, and this will be complemented by site staff, who will be trained to support parents giving the drops. Rescue analgesia with paracetamol/ibuprofen will be permitted and measured, with parents being asked to record if being used for analgesia, fever or both.

Clinicians will receive (from the study team) clear instructions regarding the importance of not administering ear drops in the presence of any ear discharge, which may be indicative of tympanic membrane perforation (and in which case there is a theoretical but unconfirmed risk of ototoxicity), and these instructions will be passed on by clinicians to parents as part of the trial recruitment processes.

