7.4. Dosing regimen

According to the randomisation schedule for the full trial, a child participating in the RCT will receive either active ear drops, placebo ear drops or no drops (children participating in the initial 2 arm pilot will receive either active ear drops or no ear drops). Children participating in the OCS will not receive any ear drops.

For children allocated to either of the two treatment arms within the RCT (active ear drops plus usual care, or placebo ear drops plus usual care), the allocation will be unknown to the clinician, parent, child and to the research team (with the exception of the Trial Pharmacist at UH Bristol Pharmacy). For children recruited during the 2 arm pilot, allocation to active ear drops will be known at the point of recruitment, following the assessment of eligibility and informed consent processes.

Regardless of allocation, parents in the two treatment arms will be asked to administer the ear drops no more than every 2 hours and a maximum of 12 times daily, in one or both ears to a maximum age-specific dosage per child, until pain is relieved, and for a maximum of 8 days. Missed doses should not be compensated for by giving a larger dose or more frequent doses. Clear dosage instructions will be provided on the medicine bottle and in the trial instructions for parents on how to give ear drops.

We anticipate that for 50% of children the duration of treatment until pain relieved will be 3 days, and that 90% of children's symptoms will have resolved by 8 days¹⁷.

There are no special dietary or other requirements to be imposed.

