- Hyaluronidase effectively increases the diffusion of local anesthetics. The beneficial effects of hyaluronidase are offset by an increased incidence of systemic toxic reactions due to increased absorption of the local anesthetic
- St John's Wort may increase the risk of cardiovascular collapse and/or delayed emergence from anesthesia

Adverse reactions

Due to its low aqueous solubility, benzocaine is poorly absorbed and systemic toxicity is rare however, methemoglobinemia has been observed following topical application.

Benzocaine may cause the following symptoms: nausea and vomiting, whereas, Phenazone has been associated with the haemolytic anemia and agranulocytosis. Such reactions are unlikely following application of Auralgan on the external ear canal.

Hypersensitivity reaction consisting of rash, urticaria, oedema, anaphylaxis have been observed rarely with Benzocaine.

Symptoms such as vertigo, nausea, and nystagmus has been observed after local anaesthetic use in the external or middle ear and may be due to penetration of the local anaesthetic into the inner ear.

Individuals frequently exposed to ester-type local anaesthetics can develop contact dermatitis characterised by erythema and pruritis which may progress to vesiculation and oozing. Discontinue promptly if sensitisation or irritation occurs.

Dosage and Administration

- Use Auralgan Ear Drops at room temperature.
- If bottle is cold to the touch, warm in hand for a minute.
- Tilt head to one side with affected ear uppermost.
- Fill ear canal and plug ear with cotton wool moistened with Auralgan Ear Drops.
- Repeat every 1 to 2 hours until pain is relieved.

PI- Auralgan_2015-05-07A

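### The synopsis and section 7.4 give conflicting dosing intervals for the ear drops, and the synopsis leaves out the limits that 7.4 sets

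*Protocol*

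**What the plan says.** Two parts of the current protocol state how often the drops are given.

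- **Synopsis (section 1), dosage and route row:** the drops go to the "affected ear(s) every 1 to 2 hours until pain relieved". Both ears are treated in bilateral disease. The row gives no maximum number of applications a day and no per-child maximum. The next row, on duration, has treatment continue until the pain has gone. It covers stopping after a perforation but gives no maximum number of days.
- **Section 7.4 (Dosing regimen):** parents are asked to "administer the ear drops no more than every 2 hours and a maximum of 12 times daily". The same sentence sets a ceiling per child that depends on age, whether one ear or two are treated, and limits treatment to 8 days.

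Four other places bear on the same point.

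- The lay summary (section 3) says of the drops: "They can be dropped into the ear every 1 to 2 hours".
- Section 5.6 has them given "according to the instructions provided with the medicine bottle, until pain is relieved", and states no interval or limit of its own.
- Section 9.17 attaches the 8-day maximum to the dose count for Days 2 to 7. Section 9.20 asks for the number of ear drop doses in the calls after Day 8 and does not mention that maximum.
- Appendix 8 reproduces the manufacturer's product information, which reads "Repeat every 1 to 2 hours until pain is relieved".

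**The concern.** A clinician who reads the synopsis and one who reads section 7.4 come away with different rules for the same child. The protocol itself treats exposure to benzocaine as a safety matter. Section 6.1 justifies the lower age limit by the risk of methaemoglobinaemia, and section 7.9 lists the signs that clinicians and parents should watch for. Recruiting clinicians train parents to give the drops (sections 6.11 and 9.10), so a discrepancy in the protocol could be passed on to families. A dosing rule in a paediatric drug trial should read the same wherever it is stated.

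**Working it through.** **Inputs**

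| Item | Synopsis | Section 7.4 |
|---|---|---|
| Shortest permitted interval | 1 hour | 2 hours |
| Maximum applications a day | not stated | 12 |
| Age-specific maximum per child | not stated | stated to exist, no figure |
| Maximum duration | not stated | 8 days |
| Stopping when pain is relieved | yes | yes |

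**Step 1: reproduce the plan's own figure.** Applications per day = 24 h / interval. At the 2-hour interval in section 7.4, 24 / 2 = 12, which is exactly the stated daily maximum. Section 7.4 is therefore consistent within itself.

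**Step 2: apply the same formula to the synopsis range.**

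| Interval | Applications a day | Ratio to 12 |
|---|---|---|
| 2 h | 24 / 2 = 12 | 1.0 |
| 1.5 h | 24 / 1.5 = 16 | 1.33 |
| 1 h | 24 / 1 = 24 | 2.0 |

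The two texts agree only at the 2-hour end of the range. Any shorter interval follows the synopsis and breaks section 7.4.

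**Step 3: vary the assumptions.** If the drops were given only during an assumed 16 waking hours, the counts would be 16 / 1 = 16 against 16 / 2 = 8. The ratio is again 2, and 16 is still above the daily maximum of 12. Over 8 full days the ceilings are 24 × 8 = 192 and 12 × 8 = 96.

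**Step 4: separate conflict from omission.** The interval is stated in both places with different values, which is a conflict. The daily, age-specific and duration limits are stated only in section 7.4, so for those the synopsis is incomplete.

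**What cannot be computed.** The age-specific maximum is not given as a figure, so these counts of applications cannot be turned into an excess amount of drug.

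**The case against.** The strongest reply is that parents do not dose from the synopsis. Section 7.4 promises clear instructions on the bottle and in the parent materials, and section 9.10 adds clinician training, printed instructions and a video. Section 7.4 is also the only section devoted to the regimen, and a synopsis row may reasonably leave out detail. This lowers the practical risk and explains the missing limits. It does not explain an interval that differs from the one in section 7.4.

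A reader might infer several stronger points that the documents do not support.

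- **That the limits themselves contradict each other.** The synopsis gives no competing values.
- **That section 5.6 sends parents to the commercial leaflet.** Section 7.2 has the supplier pack and label the bottles for the trial, and 7.4 puts the dosage instructions on the bottle. The phrase "according to the instructions provided with the medicine bottle" can therefore mean the trial label. It is unclear rather than wrong.
- **That the lay summary prescribes hourly dosing.** Its sentence goes on to over-the-counter availability abroad and largely describes the marketed product.
- **That Appendix 8 is in error.** It is the manufacturer's own text, appended for reference.
- **That section 9.20 permits dosing after Day 8.** Asking about doses collects data and may serve to detect use beyond the maximum.
- **That the adherence data lose their reference regimen.** Section 7.6 measures adherence by reported administrations and bottle weight, and scores neither against an interval.
- **That the amendment history settles the matter.** It records that section 7.4 was clarified in version 1.3. That may explain how the texts came to differ, but both are now current, and this review does not choose between them.

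**Conclusion.** The point holds for the synopsis against section 7.4. The dosing intervals conflict directly, and the synopsis omits the daily, age-specific and duration limits. The size is at most two-fold in applications per day (24 against 12). That ceiling assumes hourly dosing around the clock by someone following the synopsis. It falls to no difference at the 2-hour end of the range. Nothing in the protocol shows that any child would be dosed this way, and the label, parent sheet and video are not available to check. Even so, a safety-relevant dosing rule is stated inconsistently, the conflict is plain on the page, and the correction is cheap. It should be made.

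**What to change.** Reconcile the synopsis rows on dosage and duration with section 7.4, so that one interval and one set of limits appear throughout. Which regimen applies is for the clinical team and the Trial Steering Committee to confirm.

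For consistency, in the same revision:

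- align the lay summary wording with the agreed text, or make clear that it describes the marketed product;
- state in section 5.6 which bottle instructions are meant;
- state in section 9.20 why ear drop doses are asked for after Day 8, given the 8-day maximum in sections 7.4 and 9.17;
- check that the bottle label, parent instructions and training video carry the agreed text.

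Appendix 8 needs no change. The cost is a text correction and a check of the parent-facing materials. No design, sample size or analysis changes.
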